In addition, we will run a linear regression model with mode, agent and a mode by agent interaction term to assess whether an interaction between mode and agent exists. In the unlikely event that randomization was not able to reduce bias by balancing out confounders, we will assess for confounding. This will be carried out by assessing each potential confounder individually in relation to the key predictor (mode or agent) and seeing if the potential confounder impacts the parameter estimate of the key predictor using the 10% change in estimate approach. The potential confounder would also need to be significantly related to the EPDS score outcome. Should any confounders exist, they'll will be included in all of the previously mentioned analyses. Rules on the number of variables allowed in a multivariable model will be followed. The rule on number of variables in a linear regression is to take the total number of observations divided by 10. Given our trial sample size, we will not have any concerns with overfitting our linear model for our covariates of interest (education level, marital status, ethnicity, baseline severity and chronicity, timing of treatment, compliance, perceived support and medication).

Our study statistician and two independent methodological consultants have reviewed and approved this plan of analysis.

**3.5.2. Secondary Analysis.** In our secondary analysis, we are interested in: i) assessing the trend in EPDS scores over time (baseline, 3, 6- and 12-months post-randomization) between

groups (telemedicine vs in-person, and specialist vs NSP). This will involve the use of linear mixed models adjusting for possible covariates including baseline depression symptoms, medication, treatment dosage, and child age when assessing child outcomes. Mothers will be taken as a random effect and the models will include a treatment- by- time interaction term; ii) the same set of analyses will be conducted for anxiety symptoms (GAD-7). All child outcomes, including child mental development and the provision of psychosocial stimulation by the mother, will be compared between two groups (antenatal vs. postnatal) at 6-24 months post-childbirth using a two-sample two-sided t-test. Sensitivity analyses will be carried out excluding those who dropped out after first session to see if the results are comparable to the entire study group. No interim analyses will be carried out.

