1.1. Principal Research Objectives

The primary objectives of this trial are to:

- Examine if a brief, BA psychological treatment delivered by non-specialist providers (NSP) is as effective in treating perinatal depressive symptoms as specialist-delivered treatment* (*Primary Aim 1*); and
- Examine if a brief BA psychological treatment delivered through telemedicine (TM) is as effective in treating perinatal depressive symptoms as in-person treatment (IP; *Primary Aim 2*)*.

*Note: 'as effective' is the language that we used in the PCORI submission and what PCORI would like to see when they review this document. After consultations with several statistical experts, we will cater the language accordingly for the audience e.g., use 'non-inferior' for academic audiences and the current language for lay audiences.

The primary hypotheses are that among mothers with depressive and anxiety symptoms, psychological treatment delivered by NSPs will be as effective as treatment delivered by specialist providers. In addition, psychological treatment delivered via TM will be as effective as in-person treatment at 3-months, post randomization.

[figure not shown]
The secondary objectives are to:

- Examine the aforementioned questions for anxiety symptoms at 3-months post randomization (*Secondary Aim 1*);
- Assess moderating effects of clinical severity (mild, moderate and severe) on the comparative effectiveness of the two delivery modes on depressive and anxiety symptoms at 3-, 6- and 12-months post randomization (*Secondary Aim 2*);
- Explore whether the timing of the treatment (antenatal vs. postnatal) influences depressive and anxiety symptoms at 12-months post-randomization, and separately, on child mental development at 6 to 24 months post childbirth (*Secondary Aim 3*); and
- Conduct a process evaluation, i.e., identify the underlying processes related to delivery and scalability of a brief psychological treatment for perinatal depressive and anxiety symptoms from a multi-stakeholder perspective, including relevant barriers and facilitators (*Secondary Aim 4*).

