3.1. Recruitment and Representativeness of Recruited Participants

Initial analyses will include examining the number of:

- patients that declined to consent and reasons,
- participants that consented, and
- eligible participants.

Analyses will also be conducted by intervention arm, examining the number of:

- participants allocated to each arm,
- participants that completed treatment and treatment compliance, and
- participants that completed the 3-, 6- and 12-months post-treatment assessments.

Recruitment data and representativeness of recruited participants are collected in the CONSORT flow chart. Participants are consented and randomized to one of the four arms at each of the 5 sites [Sinai Health, Women's College Hospital, St. Michael's Hospital (referral-site only), UNC, NorthShore] within the 3 Hubs (Toronto, Chicago, Chapel Hill). However, given the availability of treatment providers, patients may be referred to another site to enroll and randomize (in

Toronto, only). In this event, the collected data will be adjusted for site correlations due to potential site differences.

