Aim 2 is to show that TM is non-inferior to in-person (N=268 per group, IP vs TM, [Table 4](#)).

Aim 1 and Aim 2 will initially be analyzed using a non-inferiority t-test (under the assumption that randomization will serve to balance out potential confounders). Each t-test will look at the confidence interval around the difference in EPDS scores (say between TM and IP) and see if the upper bound contains the non-inferiority margin (upper bound for the case in which we take the difference to be TM minus IP). In addition, we will run a linear regression model with mode, agent, and a mode by agent interaction term to assess whether an interaction between mode and agent exists. In the unlikely event that randomization was not able to reduce bias by balancing out confounders, we will adjust for variables found to be imbalanced at baseline.

Rules on the number of variables allowed in a multivariable model will be followed. The rule on number of variables in a **linear** regression is to take the total number of observations divided by 10. Given our trial sample size, we do not have any concerns with overfitting our linear model for our **covariates of interest** (education level, marital status, ethnicity, baseline severity and chronicity, timing of treatment, compliance, perceived support, and medication). For the **logistic** regression analyses, the number of predictors will be based on the smaller of the two outcome categories divided by 10^{36} .

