3.4.1.1. COVID-related Adjustments (Phase Analysis)

In order to determine whether the participants recruited in Phase 2 can be combined with those in Phase 3 in the larger trial, we will examine a potential interaction between group (SP, NSP) and phase (2 and 3) in relation to change in EPDS and GAD scores. To examine this, a linear mixed model will be run for the outcome EPDS and another for the outcome GAD. Each model will contain a group (SP, NSP), Phase (2 and 3), and a group by phase interaction term. A comparison of Phase 1 (pre COVID phase) to Phase 3 (return to IP phase) will not be carried out as the sample size in the first phase (n=23) is too small to detect statistical differences; however, we will conduct a sensitivity analysis on our primary outcome (EPDS scores at 3-month post-randomization) which includes this portion of the sample.

The study analyses will be carried out as originally planned on the entire sample of participants across all 3 phases. Should we find a group by phase interaction, we will also run separate analyses by phase (2 and 3) and compare their results to the model on the entire sample.

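### The primary telemedicine versus in-person test pools periods when mode was not randomised; on the planned 958/268 split at least about 72% of telemedicine participants are expected to lack a concurrent in-person comparator

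*SAP*

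**What the plan says.** SAP 3.4.1 says that both primary aims "will initially be analyzed using a non-inferiority t-test (under the assumption that randomization will serve to balance out potential confounders"). Protocol 3.5.1 likewise plans one t-test for mode and one for provider. SAP 3.4.1.1 fixes the analysis set: "The study analyses will be carried out as originally planned on the entire sample of participants across all 3 phases".

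SAP 1.5 and Protocol 2.2.3.2 describe how mode was allocated:
- four arms at 1:1:1:1 in Phase 1;
- TM only in Phase 2;
- 3:1 in favour of IP in Phase 3;
- TM only again during the Omicron wave;
- then 1:1:1:1, with sites allowed to drop to TM only under local restrictions;
- TM only once the IP arms are full.

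Provider type stayed 1:1 throughout. SAP 1.6.2 plans 958 TM and 268 IP.

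Several provisions touch on confounding:
- SAP 3.4.1: if randomisation fails to balance confounders, "we will adjust for variables found to be imbalanced at baseline".
- Protocol 3.5.1: "assessing each potential confounder individually in relation to the key predictor (mode or agent"), with a 10% change-in-estimate criterion. It adds: "The potential confounder would also need to be significantly related to the EPDS score outcome".
- SAP 3.4.1.1: analyses by phase, if provider group interacts with Phase 2 versus 3.
- SAP 1.2: site is considered as a possible covariate. SAP 3.1, for patients referred across sites: "the collected data will be adjusted for site correlations due to potential site differences".
- Protocol 3.5.1 and SAP Table 6: comparisons of symptom scores between COVID periods.

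**The concern.** A participant enrolled in a TM-only period had no chance of being allocated to IP. Pooling such participants with the IP arm makes the mode contrast partly a comparison of calendar periods and site mixes. Pooling 1:1 and 3:1 recruitment without stratifying also ties mode to period, even within four-arm recruitment. The stated reason for an unadjusted t-test is therefore false for mode.

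One of the two primary conclusions is at stake. If 3-month EPDS drifted over the pandemic, Aim 2 could show false non-inferiority or fail wrongly, depending on the direction. The SAP treats period as a live question for provider type and for baseline symptoms, but does not ask it of the mode contrast.

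**Working it through.** **Plan's own totals (SAP 1.6).** 431/0.9 = 479 per provider group, and 2 × 479 = 958. 241/0.9 = 268 IP. 958 + 268 = 1,226, as stated. (Separately, a margin of 1.03 at one-sided 0.05 needs 256 per group, not 241. With the resulting 285 IP, the 1:1 share below would be (958 − 285)/958 = 70%, so this barely matters here.)

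**Share of TM without a concurrent comparator.** Expected concurrent TM = (IP enrolled at 1:1) + (IP enrolled at 3:1)/3.

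| Assumption | Concurrent TM | Non-concurrent share of 958 |
|---|---|---|
| 268 IP, all at 1:1 | 268 | 690/958 = 72% |
| 268 IP, half at 3:1 | 134 + 44.7 = 178.7 | 779.3/958 = 81% |
| 268 IP, all at 3:1 | 89.3 | 868.7/958 = 91% |
| 289 IP (21 extra), all at 1:1 | 289 | 669/958 = 70% |

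The 21 is the number of protocol deviations in SAP 3.4.1, used because the Table 5 footnote promises over-recruitment for them. Apart from n=23 in Phase 1, the documents give no counts by phase, so these are planning expectations.

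**Illustration with no safeguard acting.** Evaluable 862 TM and 241 IP, SD 4.68, margin 0.13 × 7.93 = 1.031, success judged on the 95% CI. SE = 4.68 × √(1/862 + 1/241) = 0.341. Let d be an assumed average 3-month EPDS difference between non-concurrent and concurrent TM; bias = 0.72 × d.

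- False non-inferiority at the margin, bias favouring TM: Φ(bias/SE − 1.96).
- Power at no true difference, bias against TM: Φ((1.031 − bias)/SE − 1.96).

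| d | Bias | False non-inferiority | Power |
|---|---|---|---|
| 0 | 0 | 2.5% | 86% |
| 0.5 | 0.36 | 18% | 50% |
| 1 | 0.72 | 56% | 15% |

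**Would the Protocol's confounder rule catch it?** Suppose period were tested. Non-concurrent evaluable TM = 862 − 241 = 621; mixed periods hold 241 + 241 = 482. The chance that period is significantly related to EPDS is Φ(d/SE − 1.96), with no mode effect:
- TM-only versus mixed periods (621 vs 482, SE 0.284): 42% at d = 0.5, 94% at d = 1.
- Within TM (621 vs 241, SE 0.355): 29% and 80%.

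At the margin the first test is weaker, because the mixed group contains IP. Taking the IP mean as 0, mixed periods average 1.031/2 = 0.515 and non-concurrent TM averages 1.031 − d. The gap is 0.016 at d = 0.5 and 0.485 at d = 1, giving detection of about 5% and 40%.

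**Power of a concurrent comparison** (margin 1.03, no true difference):

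| Evaluable set | SE | One-sided 0.05 | 95% CI rule |
|---|---|---|---|
| All IP at 1:1 (241 vs 241) | 0.426 | 78% | 68% |
| Half of IP at 3:1 (strata 120.5 vs 120.5 and 120.5 vs 40.2, inverse-variance) | 0.492 | 67% | 55% |
| All IP at 3:1 (241 vs 80) | 0.603 | 53% | 40% |

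**The case against.** The best defence is that the plan already has routes to adjustment. The SAP rule on baseline imbalance needs no test against EPDS. If enrolment period counted as such a variable, its imbalance between TM and IP would be extreme and adjustment almost certain. The Protocol's rule could also admit period, and at a drift of 1 point usually would when there is no mode effect. So a reader might infer from the 18% and 56% that these are the trial's error rates. They are not: they assume no safeguard acts and a drift that the documents do not report.

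A reader might also infer that period is never examined. That is wrong too: SAP 3.4.1.1 fits a phase term for EPDS, and the COVID comparisons are planned.

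What survives is narrower. Neither document names period as a covariate for mode. The timing-of-treatment item in the covariate list appears to mean perinatal period, as in SAP 1.1: "Explore whether the timing of the treatment (antenatal vs. postnatal) influences depressive and anxiety symptoms". The trigger for by-phase analysis is a provider-by-phase interaction, which does not address mode, and Phase 2 has no randomised IP arm to analyse. The COVID comparisons leave the mode estimate unchanged. Site is only considered, or adjusted for cross-site referrals, and site alone does not remove period.

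One could also read "Aim 2 is to show that TM is non-inferior to in-person (N=268 per group, IP vs TM") as a matched subset. It cites Table 4, gives no selection rule, and sits beside the whole-sample statement, so it is better read as a power requirement.

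The loss of power under a concurrent analysis is real. However, the pooled test's 86% holds only if there is no period effect.

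**Conclusion.** The point stands and should be fixed. The assumption behind the primary Aim 2 test holds for provider type but not for mode, and no written safeguard reliably repairs this. The expected non-concurrent share of TM is 72% to 91% on the 958/268 plan, or about 70% with 21 extra IP at 1:1.

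That share depends on 958/268 being the split analysed. Protocol 2.8 promises equal arms, and SAP 1.5 gives equal IP and TM numbers as the purpose of the 3:1 weighting. Under equal numbers these percentages would not apply, though TM-only periods would still lack an IP comparator. The share also takes SAP 1.5 as the record of Phase 2; SAP Table 6 instead describes that phase as one in which IP allocation was treated as TM.

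The documents do not show that Aim 2 is biased, or in which direction. They support the conclusion that the planned test is exposed to period bias and that adjustment for it is left to chance.

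**What to change.** In SAP 3.4.1 and 3.4.1.1 and Protocol 3.5.1:

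1. Make the primary Aim 2 estimate TM minus IP from a linear model with terms for site, randomisation period (intervals with a single allocation ratio, defined within site) and perinatal stratum. Only participants randomised while both modes were open at their site then inform the mode contrast. Apply this to both the intent-to-treat and per-protocol analyses.
2. Keep the whole-sample t-test as a sensitivity analysis, and leave Aim 1 on the full sample.
3. Remove the statement that randomisation balances TM versus IP over the whole sample.
4. Restate Aim 2 power for the concurrent set, using the actual counts by allocation ratio.
5. Record the date of the change, and label it post hoc if outcomes have been unblinded. The documents do not say whether they have; the current protocol version is dated 25 Oct 2024, after the stated study end of 31 May 2024.

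The cost is wording plus a table of the allocation ratio in force by site and date, with no new assessments. The interval will be wider than the pooled one. Adding baseline severity, already a covariate of interest, would recover some precision: at an assumed correlation of 0.2 to 0.5 with 3-month EPDS, power under the 95% CI rule at 241 versus 241 becomes 69% to 80%.

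As supporting clean-up, reconcile the 268 per group, the equal-numbers text and the two descriptions of Phase 2 with the 958/268 plan.

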3.4.2. Secondary Analysis

3.4.2.1. Analysis for Secondary Aim 1: Anxiety Symptoms

In our secondary analysis, we are interested in **examining the primary questions for anxiety symptoms at 3-months post randomization.**

This aim is to show that NSP is non-inferior to SP. One t-test will be run to assess this and compare agents (is NSP non-inferior to SP). This aim is to also show that TM is non-inferior to in-person. Another t-test will be run to assess this and compare modes (is TM non-inferior to IP). We will require a sample of 774 participants and use a NIM of 10% for NSP compared to SP which translates to a mean EPDS difference of 0.871 based on the mean of 8.71 (SD=4.61)³⁷ and 10% dropout. On the other hand, a sample of 460 participants and a NIM of 13% will be required for TM compared to IP which translates to a mean difference of 1.142 based on the

mean of 8.71 (SD=4.61)³⁷ and 10% dropout. In addition, we will run a linear regression model with mode, agent, and a mode by agent interaction term to assess whether an interaction between mode and agent exists.

No interim analyses will be carried out.

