1.6.1. Primary Aim 1 (Specialist vs. Non-Specialist) Comparison

The primary outcome measure is an EPDS mean score at 3 months post-randomization. The sample size calculation is based on an EPDS mean estimate of 7.93 (SD=4.68)³⁰. Using a non-inferiority margin of 10% (i.e., EPDS score of 0.79 in relation to the mean), and an alpha=0.05, we require 431 participants in each of the two groups (SP, NSP) to provide greater than 80% power ([Table 3](#)). To account for 10% drop out, the sample size is inflated to **N=958** (479 per group, SP vs. NSP). All sample size calculations were run using PASS Version 12³¹.

Table 3: Power Analysis of a Non-Inferiority Test of the Difference of Two Means

Power	N1/N2	Non-Inferiority Margin (NIM)	Actual Difference	Significance Level (Alpha)	Beta	Standard Deviation 1 (SD1)	Standard Deviation 2 (SD2)
0.80022	431/431	0.793	0.000	0.05000	0.19978	4.680	4.680

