1.6.2. Primary Aim 2 (Telemedicine vs. In-Person) Comparison

The primary outcome measure is an EPDS mean score at 3 months post-randomization. The sample size calculation is based on an EPDS mean estimate of 7.93 (SD=4.68)³⁰. Using a non-inferiority margin of 13% (i.e., EPDS score of 1.03 in relation to the mean), and an alpha=0.05, we require an additional 268 IP participants ([Table 4](#)).

Table 4: Non-inferiority margin in relation to sample size for Phase 3 comparisons

Non-inferiority margin	Power	Sample size per primary question	Total sample size + 10% dropout*	Total sample size + 20% dropout
10%	80%	431	958	1078
13%	80%	241	536 (268 per group)	604
14%	80%	221	492 (246 per group)	556

*Current dropout rates are <10% at primary outcome of 3-months post-randomization

When combined with the 958 TM participants, this yields a total study sample size of N=1,226 which accounts for 10% loss to follow-up ([Table 5](#)).

Table 5: Primary aims and required sample sizes

Primary Aim [¥]	Non-inferiority Margin	Power	Required sample size + 10% drop out
SP vs. NSP [¥]	10%	88%	958 telemedicine
IP vs. Telemedicine	13%	80%	268 in-person*
	Total		N=1226*

[¥]We acknowledge that the in-person sample is contained in the first hypothesis. This will result in the SP vs NSP comparison having up to 88% power. *We will over-recruit to account for protocol deviations where participants were switched from in-person to telemedicine due to the COVID-19 pandemic.

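### SAP 3.4.2.1 gives the telemedicine versus in-person anxiety margin two values: 13% of 8.71 is 1.132 points, but 1.142 is printed

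*SAP*

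**What the plan says.** SAP 3.4.2.1 plans two non-inferiority t-tests on anxiety symptoms at 3 months and gives each a relative margin, a margin in score points and a total sample size.

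- Non-specialist (NSP) versus specialist (SP) providers: a total of 774 and a 10% margin, "which translates to a mean EPDS difference of 0.871 based on the mean of 8.71".
- TM versus IP: a total of 460 and a 13% margin. The points value is given in the words "which translates to a mean difference of 1.142 based on the", referring to the same planning figure.
- Both rest on a "mean of 8.71 (SD=4.61)³⁷ and 10% dropout".

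The section does not state alpha, power, the assumed true difference or the allocation. The general rule in SAP 3.4.1 declares success when the upper limit of the 95% confidence interval does not exceed the margin. No other place in the protocol or SAP gives the anxiety margins in score points.

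**The concern.** The two expressions of the TM versus IP margin should be the same number, and they are not. The companion margin in the same paragraph is exact (10% of 8.71 is 0.871), so a different rounding convention does not explain the gap.

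The margin is what the confidence limit is compared with, and Secondary Aim 1 is a stated objective. If the limit fell between 1.132 and 1.142, the result would depend on which expression the analyst used. Separately, the only instrument that the paragraph names beside either margin is the EPDS, in a section about anxiety.

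**Working it through.** **Inputs**

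- Mean 8.71, SD 4.61, dropout 10%, margins 10% and 13%, totals 774 and 460: SAP 3.4.2.1.
- Alpha 0.05: carried over from SAP 1.6.2 ("and an alpha=0.05, we require an additional 268 IP participants"). It reproduces the anxiety totals only if used one-sided.
- Power 80%: carried over from SAP 1.6.1 ("to provide greater than 80% power").
- True difference 0: SAP Table 3 lists 0.000 under "Actual Difference". Assumed to apply here too.
- Equal allocation: assumed, as in the primary TM versus IP calculation.

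**Step 1. The product**

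- 0.10 × 8.71 = 0.871, as printed.
- 0.13 × 8.71 = 1.1323, printed as 1.142.
- 1.142 / 8.71 = 0.1311, that is 13.11%.
- Gap: 1.142 − 1.1323 = 0.0097 points, and 0.0097 / 1.1323 = 0.9%.
- For 1.142 to be 13% of the mean, the mean would have to be 1.142 / 0.13 = 8.78. The documents give no such mean.

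**Step 2. Reproduce the plan's own totals**

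The normal approximation per group is n = 2 × (SD / margin)² × (1.645 + 0.842)², where the last factor is 6.183. The exact version uses the noncentral t distribution. Dropout is applied as n / 0.9, rounded up, then doubled.

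Method check on NSP versus SP, margin 0.871:

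- Normal: 2 × (4.61 / 0.871)² × 6.183 = 346.4, so 347 per group.
- Exact t: 348 per group; 348 / 0.9 = 386.7, so 387; total 774. This matches the SAP.

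TM versus IP by the exact t, against the stated 460:

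| Margin | Evaluable per group | Per group after dropout | Total |
|---|---|---|---|
| 1.13 (13% rounded to two decimals) | 207 | 230 | 460 |
| 1.132 | 206 | 229 | 458 |
| 1.142 | 203 | 226 | 452 |

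The normal approximation gives 205.0 per group (total 456) for 1.1323 and 201.5, rounded up to 202 (total 450), for 1.142.

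**Step 3. Power at the stated total**

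460 × 0.9 = 414 evaluable, or 207 per group. Exact t power is 80.2% with 1.132 and 80.8% with 1.142, a difference of about 0.6 percentage points.

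**Step 4. Sensitivity to the assumed alpha**

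With one-sided 0.025 the totals become 980 for margin 0.871 and 572 for margin 1.142 (exact t). Neither stated total is reproduced, so one-sided 0.05 is the setting behind the SAP's figures.

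**Step 5. The scale label**

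The SAP's EPDS planning mean is 7.93 (SD 4.68; SAP 1.6.1), not 8.71. Anxiety is measured by the GAD-7 in SAP Table 2, SAP 3.4.2.2, SAP Appendix 1 and Protocol 1.4.2. SAP 3.4.2.1 itself never names the GAD-7.

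**The case against.** The strongest reply is that nothing of substance turns on this. The SAP expresses its margins as percentages throughout, and the points figure appears in a sample-size sentence as a translation of the 13%. An analyst could reasonably treat 13% as governing and 1.142 as a typing slip, since it differs from 1.132 in one digit. The outcome is secondary, and the conclusion changes only if the confidence limit falls in a window of about 0.01 points. The planned 268 in-person participants already exceed the 230 per group implied by 460. The EPDS label is a wording error that the section heading makes evident. All of this stands as an argument about size. It does not make the two figures agree, and nothing elsewhere in the documents corrects either the figure or the label.

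A reader might infer two stronger things, and the documents support neither.

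- *That 1.142 contradicts its own sample size.* It gives 452, which is 8 below the stated 460 (1.7%), and 460 gives more than 80% power with it. The 1.132 figure does not give exactly 460 either. The exact match with 1.13 suggests that the calculation used the correct product and that only the printed figure is wrong. That is indirect support; the proof of the error is the multiplication.
- *That the trial's decision threshold is too wide.* The documents do not establish that 1.142, and not 13%, is the operative cut-off. They show one margin stated in two ways that differ slightly.

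**Conclusion.** The point holds as a minor inconsistency. SAP 3.4.2.1 gives the TM versus IP anxiety margin as 13% of 8.71, which is 1.132, and also as 1.142. The excess is 0.0097 points, or 0.9% of the margin. This rests only on the SAP's own mean and percentage.

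The finding that 460 suffices under either value rests on the carried-over assumptions: one-sided alpha 0.05, 80% power, true difference 0, SD 4.61, equal groups and 10% dropout. If the 95% interval in SAP 3.4.1 is two-sided, its upper limit corresponds to one-sided 0.025, and about 584 would be needed with 1.132. That is a separate question about the alpha used in planning, and correcting this figure neither causes nor cures it.

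The EPDS label on 0.871 is a second, independent wording error. It adds no weight to the arithmetic point.

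**What to change.** In SAP 3.4.2.1:

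1. Replace 1.142 with 1.132, so that the percentage and the points value agree before analysis.
2. Change the scale named beside 0.871 from EPDS to GAD-7, and name the GAD-7 beside 1.132 as well. When doing so, confirm from the cited source that 8.71 (SD 4.61) is a GAD-7 mean, because the section does not say so.

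The stated totals of 774 and 460 can stay. The cost is an edit of one or two lines, with no change to sample size, recruitment or analysis method.
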